13.2 Appendix: World Health Organization Classification of Topical Corticosteroids

The potency of a topical corticosteroid depends on the formulation. Potency is also increased when a formulation is used under occlusive dressing or in intertriginous areas. In general, ointments are more potent than creams or lotions.

Table 13-2 WHO Classification of Topical Corticosteroids

Ultra-High Potency
Group I
Clobetasol propionate cream (0.05%)
Diflorasone diacetate ointment (0.05%)
High Potency
Group II
Amcinonide ointment (0.1%)
Betamethasone dipropionate ointment (0.05%)
Desoximetasone (cream or ointment) (0.025%)
Fluocinonide (cream, ointment, or gel) (0.05%)
Halcinonide cream (0.1%)
Group III
Betamethasone dipropionate cream (0.05%)
Betamethasone valerate ointment (0.1%)
Diflorasone diacetate cream (0.05%)
Triamcinolone acetonide ointment (0.1%)
Moderate Potency
Group IV
Desoximetasone cream (0.05%)
Fluocinonide acetonide ointment (0.025%)
Hydrocortisone valerate ointment (0.2%)
Triamcinolone acetonide cream (0.1%)

Moderate Potency (continued)

Group V

- Betamethasone dipropionate lotion (0.02%)
- Betamethasone valerate cream (0.1%)
- Fluocinonide acetonide cream (0.025%)
- Hydrocortisone butyrate cream (0.1%)
- Hydrocortisone valerate cream (0.2%)
- Triamcinolone acetonide lotion (0.1%)

Low Potency

Group VI

- Betamethasone valerate lotion (0.05%)
- Desonide cream (0.05%)
- Fluocinolone acetonide solution (0.01%)

Group VII

- Dexamethasone sodium phosphate cream (0.1%)
- Hydrocortisone acetate cream (1%)
- Methylprednisolone acetate cream (0.25%)

Source: Bolognia JL, Jorizzo JL, Schaffer JV. Glucocorticosteroids. Dermatology. 3rd ed. 2012. Ch 125, 2075-88.

Table 9	MedDRA Internationally Agreed SOC Order.....	78
Table 10	Safety Laboratory Parameters and Units.....	79

Table of Figures

Figure 1	Study Schema.....	10
----------	-------------------	----

2 Abbreviations and Definitions

AE	Adverse event
BMI	Body mass index
BSA	Body surface area
BSFS	Bristol Stool Form Scale
CI	Confidence interval
CRF	Case report form
Crl	Credible interval
CRP	C-reactive protein
CSR	Clinical study report
CTCAE	Common terminology criteria for adverse events
dp	Decimal place
DIC	Deviance information criterion
DLQI	Dermatology Life Quality Index
ECOA	Electronic clinical outcome assessment
eCRF	Electronic case report form
EMICM	Expectation-maximisation iterative complex minorant
EOS	End of study
FUP	Functional uniform prior
GI	Gastrointestinal
HPD	Highest posterior density
IMP	Investigational medical product
IRT	Interactive response technology
ITT	Intention to treat
LDH	Lactate dehydrogenase
LS	Least squares
LSS	Lesion severity score
MCSE	Monte Carlo standard error
MedDRA	Medical Dictionary for Regulatory Activities
MMRM	Mixed model for repeated measures
mNAPSI	Modified Nail Psoriasis Severity Index
NPMLE	Nonparametric maximum likelihood estimator
PASI	Psoriasis Area and Severity Index
PCI	Potentially clinically important
PGA	Physician's Global Assessment
PIC	Powder in capsule
PSI	Psoriasis Symptom Inventory
PT	Preferred term
SAE	Serious adverse event
SF-36	36-Item Short Form Survey Instrument
SOC	System organ class
SAP	Statistical analysis plan
SD	Standard deviation

SE	Standard error
TEAE	Treatment emergent adverse event
ULN	Upper limit of normal
VAS	Visual analogue scale
WHO	World Health Organization

3 Introduction

The purpose of this SAP is to provide all information that is necessary to perform the required statistical analyses of study EDP1815-201. It also defines the summary TFLs to be included in the final clinical study report according to the protocol. The SAP is based upon, and assumes familiarity, with the study protocol, version 5.0, dated 17--Nov-2020.

If a future protocol amendment necessitates a substantial change to the statistical analysis of the study data, this SAP will be amended accordingly. The content of this SAP is compatible with the ICH E9 Guidance document.

4 Study Objectives and Endpoints

4.1 Study Objectives

The primary objective of the study is

- To evaluate the safety and efficacy of 3 different doses of EDP1815 for the treatment of psoriasis following daily dosing for 16 weeks.

The secondary objectives of the study are

- To evaluate the efficacy dose response of EDP1815 at Week 16.
- To evaluate the maximal clinical benefit of EDP1815 at Week 16.
- To evaluate the optimal dose of EDP1815 based on efficacy and safety up to Week 16.
- To evaluate the safety and tolerability of EDP1815 (all dose levels) throughout the study.
- To evaluate relapse and rebound of plaque psoriasis after cessation of EDP1815.

The exploratory objectives of the study are:

- To evaluate the time to onset of clinical response to EDP1815.
- To evaluate the effect of EDP1815 treatment on patient-reported outcomes including quality of life and pain.
- To evaluate the effect of EDP1815 treatment on biomarkers in blood.
- To evaluate the effect of EDP1815 treatment on biomarkers in skin plaques.
- To evaluate the effect of EDP1815 treatment on faecal microbiome composition.
- To evaluate the duration of remission, treatment success, and therapeutic effect of EDP1815.

4.2 Endpoints

The primary efficacy endpoint for the study is:

- Percentage change in PASI score from baseline at Week 16.

The secondary efficacy endpoints for the study are:

- Percentage change in PASI score from baseline at Weeks 4, 8 and 12.
- Absolute change from baseline in PASI score at Weeks 4, 8, 12 and 16.
- Achievement of PASI-50 at Weeks 4, 8, 12 and 16.
- Time to first achievement of PASI-50.
- Achievement of PASI-75, PASI-90 and PASI-100 at Week 16.
- Achievement of PGA of 0 or 1 with a ≥ 2 -point improvement from baseline at Week 16.
- Achievement of PGA of 0 at Week 16.
- Percentage change from baseline in PGA*BSA at Weeks 4, 8, 12, and 16.
- Absolute change from baseline in PGA*BSA at Weeks 4, 8, 12, and 16.
- Percentage change from baseline in LSS at Weeks 4, 8, 12, and 16.
- Absolute change from baseline in LSS at Weeks 4, 8, 12, and 16.
- Percentage change from baseline in DLQI score at Weeks 4, 8, 12, and 16.
- Absolute change from baseline in DLQI score at Weeks 4, 8, 12, and 16.
- Percentage change from baseline in mNAPSI total score at Weeks 4, 8, 12, and 16.
- Absolute change from baseline in mNAPSI total score at Weeks 4, 8, 12, and 16.
- Cumulative incidence of partial relapse at Weeks 20, 24, 28, and 40.
- Cumulative incidence of complete relapse at Weeks 20, 24, 28, and 40.
- Cumulative incidence of rebound at Weeks 20, 24, 28, and 40.

Exploratory efficacy endpoints are:

- Achievement of PASI-50, PASI-75, PASI-90, and PASI-100 at Weeks 4, 8, and 12.
- Achievement of PGA of 0 or 1 with a ≥ 2 -point improvement at Weeks 4, 8, and 12.
- Achievement of PGA of 0 at Weeks 4, 8, and 12.
- Achievement of PGA of 0 or 1 at Weeks 4, 8, 12, and 16.
- Percentage change from baseline in BSA at Weeks 4, 8, 12, and 16.
- Absolute change from baseline in BSA at Weeks 4, 8, 12, and 16.
- Achievement of BSA<3% and BSA-75 at Weeks 4, 8, 12, and 16.
- Absolute change from baseline in PSI quality of life total and itch scores at Weeks 12 and 16.
- Percentage change from baseline in PSI quality of life total and itch scores at Weeks 12 and 16.
- Absolute change from baseline in Pain and Fatigue scores at Weeks 4, 8, 12, and 16.
- Percentage change from baseline in Pain and Fatigue scores at Weeks 4, 8, 12, and 16.
- Absolute change from baseline in fasting blood glucose and fasting lipid panel at Weeks 8 and 16.
- Mean duration of remission in participants who achieve PASI-100.
- Mean duration of treatment success in participants who achieve PASI-50.
- Mean duration of therapeutic effect in participants after cessation of study treatment.

Other exploratory endpoints are:

- Histological assessment of skin plaque biopsies (including epidermal thickness, basal mitotic counts and immune cell infiltrates) at Week 16 versus baseline.
- mRNA transcription analysis on skin plaque biopsies at Week 16 versus baseline.
- Blood cytokine and chemokine levels at Week 16 versus baseline.
- Microbiome composition (in faeces) at Week 16 and Week 20 versus baseline.

Note that analyses of the other exploratory endpoints will be addressed in a separate analysis plan and will not be further discussed in this document.

5 Study Methods

5.1 General Study Design and Plan

This is a multicentre, randomised double-blind, placebo-controlled, parallel cohort dose ranging study of participants with mild to moderate plaque psoriasis.

After eligibility is confirmed during the screening period ([Protocol Section 4.1](#)), participants will be randomly assigned in a 1:1:1 ratio to 1 of the following 3 parallel cohorts:

- Cohort 1: 0.8×10^{11} cells of EDP1815 or matching placebo administered as 1 PIC, once daily.
- Cohort 2: 3.2×10^{11} cells of EDP1815 or matching placebo administered as 4 PICs, once daily.
- Cohort 3: 8.0×10^{11} cells of EDP1815 or matching placebo administered as 10 PICs, once daily.

[figure not shown]
In each cohort, approximately 75 participants will be randomly assigned in a 2:1 ratio to receive either EDP1815 or matching placebo once daily for 16 weeks.

As shown in Figure 1, Part A of the study comprises a screening period of up to 4 weeks, a baseline visit, a treatment period of 16 weeks, and a follow-up visit at Week 20, making 11 scheduled study visits in total. On completion of Part A, the primary analysis will be performed.

Part B of the study is designed to assess the durability of treatment response and incidence of rebound of psoriasis following cessation of dosing. All participants will attend for skin assessments at Weeks 24 and 28, unless they have previously experienced treatment failure and/or had rebound of disease. A final visit at Week 40 will also be performed for those participants who experienced treatment response at Week 16 but have not yet met the definition of complete relapse. Part B therefore comprises a maximum of 3 additional scheduled study visits with a follow-up of up to 40 weeks (24 weeks after cessation of dosing). On completion of Part B, the final analysis will be performed.

‘Treatment failure’ is synonymous with ‘starting a new psoriasis treatment’ which is an oral agent, biological, or intermediate or high-potency dose topical therapy for plaque psoriasis. Starting topical unmedicated emollients and low-potency topical steroids which were not taken at baseline does not count as starting a new psoriasis treatment.

Figure 1 Study Schema

Note: PIC=Powder in capsule (formulation). All dosing is once daily.

Note: Since this figure was produced for the protocol, the Interim Analysis has been moved from Week 12 to when the last participant has received their last dose (Week 16).

An interim analysis will be performed after the last participant was scheduled to receive their last dose (Week 16).

Participants who withdraw from treatment in the first four weeks after randomisation may be replaced. Replacement participants will be assigned to the same cohort as the withdrawn participant but will be randomly assigned to treatment within that cohort.

5.2 Randomisation and Blinding

At the baseline visit (Visit 2), participants will be randomly allocated, in a 1:1:1 ratio to one of the three cohorts. Within the cohort, participants will then be randomly assigned in a 2:1 allocation ratio to receive either EDP1815 or matching placebo treatment.

Interactive response technology (IRT) will be used to administer the randomization schedule centrally. Successfully screened participants will be assigned to the next cohort randomisation number available at the time of their baseline visit to determine their cohort and then to the next treatment randomisation number available within that cohort.

Note that if a participant has withdrawn from treatment within 4 weeks of randomisation and is to be replaced, the next participant to be randomised will automatically be assigned to the same cohort as the participant who was withdrawn instead of being randomly assigned to a cohort. Within the cohort, the replacement participant will be randomly assigned to treatment group with the next within-cohort treatment randomisation number.

The allocation to cohort is not blinded as it is distinguishable to participants and study staff by the number of capsules administered per once-daily dose. The treatment allocation within cohort will be fully blinded to participants, study staff and the sponsor with the exception of the personnel supporting the IRT system, the clinical supplies team, the clinical safety team at [REDACTED], and an unblinded team within [REDACTED] who will produce the interim analysis but have no other involvement in the reporting of the study.

A participant's treatment assignment will not be unblinded for the investigator or study site staff until EOS unless medical treatment of the participant depends on knowing the study treatment the participant received. Participants who are unblinded will be allowed to continue their participation in the study; however, any data collected after the unblinding occurred will be excluded from per-protocol analyses.

For the interim analysis, unblinded aggregate results will be produced by the unblinded team within [REDACTED] and reviewed by EVELO personnel for strategic planning use. These results will not be shared with study site staff, participants, or clinical monitors who will be involved in the collection and review of individual study data.

The data will be unblinded and the primary analysis will be performed once all participants have completed 4 weeks of post-treatment follow-up at Visit 11 (Week 20; at the end of Part A). Study site staff, participants, and clinical monitors who will be involved in the collection and review of individual study data will remain blinded until Part B is completed.

5.3 Derived variables

5.3.1 General

5.3.1.1 Relative Day and Time

The relative day of an assessment will be calculated as:

- For measurement performed on or after the date of first dose:
Date of assessment – date of start of treatment +1
- For measurements performed before the date of first dose:
Date of assessment – date of study treatment

5.3.1.2 Baseline

The last non-missing value collected before first study dose will be taken as the baseline measurement for all parameters. If data is collected on Day 1 without an associated time being provided, it will be assumed to be pre-dose. Efficacy data collected using the electronic clinical outcome assessment (eCOA) device on the same day as the first dose of study medication will also be assumed to be pre-dose data and can be used for the baseline assessment, regardless of whether the time indicates if it was before or after the time of first dose.

5.3.1.3 Change and Percentage Change from Baseline

Change from baseline will be calculated as:

$$\text{change from baseline} = \text{value at timepoint} - \text{baseline value}$$

Change from baseline will be presented to the same level of precision as the original value in the listings.

Percentage change from baseline will be calculated as:

$$\text{percentage change from baseline} = 100 * (\text{change from baseline} / \text{baseline value})$$

Percentage change from baseline will be presented to 1 decimal place (dp) in the listings.

5.3.2 Demographic and Background Data

Height may be recorded in cm or inches. Height in inches will be converted to height in cm as follows:

$$\text{Height (cm)} = \text{Height (inches)} * 0.3937$$

Height (cm) will be presented to 1 dp in the listings.

Weight may be recorded in kg or pounds. Weight in pounds will be converted to weight in kg as follows:

$$\text{Weight (kg)} = \text{Weight (pounds)} * 0.4536$$

Weight (kg) will be presented to 1 dp in the listings.

Body mass index (BMI) will be calculated as:

$$\text{BMI (kg/m}^2\text{)} = \text{Weight (kg)} / [\text{height (cm)} / 100]^2$$

BMI (kg/m²) will be presented to 1 dp in the listings.

BMI will also be categorised as:

- $\geq 30 \text{ kg/m}^2$
- $< 30 \text{ kg/m}^2$

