7.2 Covariates and Subgroups

If the placebo groups from the 3 cohorts are found to be too heterogeneous to be pooled (see [Section 9.1](#)), the primary and secondary analyses will be performed using within-cohort comparisons of active and placebo treatments, and summary tables will also be produced by cohort.

Subgroups based on baseline severity of disease and obesity will be defined as follows:

- Using baseline PASI score ($<10, \geq 10$)
- Using baseline PGA score (2, 3)
- Using baseline BMI ($<30 \text{ kg/m}^2, \geq 30 \text{ kg/m}^2$)

For the exploratory analysis indirectly comparing the results from this study to those in the UNVEIL study ([Section 9.6.2](#)) the following subgroup of participants will be used:

- Baseline PGA=3 and Baseline BSA 5-10%

For the inferential models defined in [Section 9](#), in addition to the relevant baseline score where applicable, the following covariates will be considered:

- Body mass index (<30 kg/m², ≥30 kg/m²)
- Sex (male, female)
- Country (UK, Poland, Hungary, USA)
- Time since diagnosis (<2 years, ≥2 years)

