8.3 Demographic and Baseline Variables

Demography data of age, sex, race, ethnicity will be summarised together with height, weight and BMI at screening.

Baseline disease characteristics of time (years) since diagnosis and any current psoriasis treatment at the time of the Screening visit will be summarised.

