9.2 Selection of Additional Covariates

The covariates described in [Section 7.2](#) will be considered and included in the primary efficacy model described in [Section 9.4.3](#) for the primary estimand if found to be significant ($p<0.05$). A forward stepwise selection method will be used to include the covariates after the treatment*visit and baseline PASI score*visit interactions have already been fitted.

The covariates selected for this primary model will also be used in all other analytical models including covariates.

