9.4.5 Subgroup Analyses

The analyses described in [Section 9.4.3](#) will be repeated on the primary estimand only using the subgroups defined in [Section 7.2](#) for baseline disease severity and obesity. There will be no figures for the subgroup analyses.

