9.6 Exploratory Efficacy Analyses

9.6.1 Exploratory Efficacy Endpoints

The following exploratory endpoints will be summarised using statistics appropriate to the endpoint as described in [Section 9](#):

- Percentage of participants achieving PASI-50, PASI-75, PASI-90, and PASI-100 at Weeks 4, 8, and 12
- Percentage of participants achieving PGA of 0 or 1 with a ≥ 2 -point improvement at Weeks 4, 8, and 12
- Percentage of participants achieving PGA of 0 at Weeks 4, 8, and 12
- Percentage of participants achieving PGA of 0 or 1 at Weeks 4, 8, 12, and 16.
- Mean percentage change from baseline in BSA at Weeks 4, 8, 12, and 16.
- Mean change from baseline in BSA at Weeks 4, 8, 12, and 16.
- Percentage of participants achieving BSA<3% and BSA-75 at Weeks 4, 8, 12, and 16.
- Mean change from baseline in PSI quality of life total and itch scores at Weeks 12 and 16

- Mean percentage change from baseline in PSI quality of life total and itch scores at Weeks 12 and 16
- Mean change from baseline in Pain and Fatigue scores at Weeks 4, 8, 12, and 16
- Mean percentage change from baseline in Pain and Fatigue scores at Weeks 4, 8, 12, and 16
- Mean change from baseline in fasting blood glucose and fasting lipid panel at Weeks 8 and 16
- Mean duration of remission in participants who achieve PASI-100
- Mean duration of treatment success in participants who achieve PASI-50
- Mean duration of therapeutic effect in participants after cessation of study treatment

Note that if a participant has a zero score for any of the continuous measures (PSI score, Pain/Fatigue VAS or Bodily pain/Vitality SF-36 scores) at baseline, that participant will be excluded from any of the percentage change from baseline summaries and analyses as the percentage change from baseline cannot be calculated.

In addition to the summary statistics as described in [Section 9](#), response endpoints will also have 95% CIs presented for percentage of participants responding.

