- 4 = Moderate
- 5 = Severe
- 6 = Very severe

The Q21 score = $100 * [(6-x)/5]$ where x=1-6 is the Q21 item value as above.

Q22: During the past 4 weeks, how much did pain interfere with your normal work (including both work outside the home and housework)?

- 1 = Not at all
- 2 = A little bit
- 3 = Moderately
- 4 = Quite a bit
- 5 = Extremely

The Q22 score = $100 * [(5-x)/4]$ where x=1-5 is the Q22 item value as above.

The SF-36 bodily pain score is the average of the Q21 and Q22 scores. If at least one of the two questions have been answered, the SF-36 bodily pain score will be calculated.

Vitality score

The vitality score will be calculated from questions 23, 27, 29 and 31 of the SF-36 questionnaire:

How much of the time during the past 4 weeks...

Q23: Did you feel full of pep?

Q27: Did you have a lot of energy?

Q29: Did you feel worn out?

Q31: Did you feel tired?

Each question has possible answers (x):

- 1 = All of the time
- 2 = Most of the time
- 3 = A good bit of the time
- 4 = Some of the time
- 5 = A little of the time
- 6 = None of the time

The Q23 score = $100*[(6-x)/5]$ where x=1-6 is the Q23 item value as above.
The Q27 score = $100*[(6-x)/5]$ where x=1-6 is the Q27 item value as above.
The Q29 score = $100*[x/5]$ where x=1-6 is the Q29 item value as above.
The Q31 score = $100*[x/5]$ where x=1-6 is the Q31 item value as above.

The SF-36 vitality score is the average of the Q23, Q27, Q29 and Q31 scores. If at least two of the four questions have been answered, the SF-36 bodily pain score will be calculated.

22 Appendix 8: MedDRA Internationally Agreed Order for System Organ Class

The internationally agreed SOC order to be used for medical history and AE summary tables is provided in [Table 9](#).

Table 9 MedDRA Internationally Agreed SOC Order

Order Number	System Organ Class
1	Infections and infestations
2	Neoplasms benign, malignant and unspecified (incl cysts and polyps)
3	Blood and lymphatic system disorders
4	Immune system disorders
5	Endocrine disorders
6	Metabolism and nutrition disorders
7	Psychiatric disorders
8	Nervous system disorders
9	Eye disorders
10	Ear and labyrinth disorders
11	Cardiac disorders
12	Vascular disorders
13	Respiratory, thoracic and mediastinal disorders
14	Gastrointestinal disorders
15	Hepatobiliary disorders
16	Skin and subcutaneous tissue disorders
17	Musculoskeletal and connective tissue disorders
18	Renal and urinary disorders
19	Pregnancy, puerperium and perinatal conditions

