20	Reproductive system and breast disorders
21	Congenital, familial and genetic disorders
22	General disorders and administration site conditions
23	Investigations
24	Injury, poisoning and procedural complications
25	Surgical and medical procedures
26	Social circumstances
27	Product issues

23 Appendix 9: Safety Laboratory Evaluations

Table 10 Safety Laboratory Parameters and Units

Category	Parameter	Conventional Unit	SI Units	PCI Criteria (SI units)	
				Low	High
Hematology	Hemoglobin	g/dL	g/L	<100 ≥20 decrease from BL	>20 increase from BL
	Hematocrit	%	L/L		
	Red blood cell count	10 ⁶ /uL	10 ¹² /L		
	White blood cell count	10 ³ /uL	10 ⁹ /L	<3	
	Platelets	10 ³ /uL	10 ⁹ /L	<75	
	Mean corpuscular volume	fL	fL		
	Mean corpuscular hemoglobin	pg	pg		
	Mean corpuscular hemoglobin concentration	g/dL	g/L		
	Absolute neutrophils	10 ³ /uL	10 ⁹ /L	<1.5	
	Absolute lymphocytes	10 ³ /uL	10 ⁹ /L	<0.8	>4
	Absolute monocytes	10 ³ /uL	10 ⁹ /L		
	Absolute eosinophils	10 ³ /uL	10 ⁹ /L		
	Relative neutrophils	%	%		
	Relative lymphocytes	%	%		
	Relative monocytes	%	%		
	Relative eosinophils	%	%		
	Relative reticulocytes	%	%		

Category	Parameter	Conventional Unit	SI Units	PCI Criteria (SI units)	
				Low	High
Chemistry	Aspartate aminotransferase	U/L	U/L		>3xULN if BL did not exceed ULN, >3xBL if BL was above ULN
	Alanine aminotransferase	U/L	U/L		>3xULN if BL did not exceed ULN, >3xBL if BL was above ULN
	Creatinine	mg/dL	μmol/L		>1.5xULN if did not exceed ULN, >1.5xBL if BL was above ULN
	Potassium	mEq/L	mmol/L		>5.5
	Sodium	mEq/L	mmol/L	<125	>150
	Blood urea nitrogen	mg/dL	mmol/L		
	Total bilirubin	mg/dL	μmol/L		>1.5xULN if BL did not exceed ULN, >1.5xBL if BL was above ULN
	Direct bilirubin	mg/dL	μmol/L		
	CRP	mg/L	nmol/L		
	Creatinine kinase	U/L	U/L		>2.5xULN
	Fasting glucose	mg/dL	mmol/L	<0.17	
	Total cholesterol	mg/dL	mmol/L		>7.77
	HDL cholesterol	mg/dL	mmol/L		
	LDL cholesterol	mg/dL	mmol/L		
	Triglycerides	mg/dL	mmol/L		>3.39

Category	Parameter	Conventional Unit	SI Units	PCI Criteria (SI units)	
				Low	High
Urinalysis	Protein	mg/dL	mg/dL		
	Blood				
	Glucose	mg/dL	mg/dL		
	Ketones	mg/dL	mg/dL		
	Bilirubin				
	pH	pH	pH		
	Nitrites				
	Specific gravity				

BL=Baseline, PCI = potentially clinically important, ULN = Upper limit of normal range.

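### SAP 5.3.2 converts inches to centimetres with the inverse factor, inflating BMI 41.6-fold and placing every participant measured in inches in the BMI ≥30 subgroup

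*SAP*

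**What the plan says.** SAP section 5.3.2 permits height in either unit and gives the inch conversion as "Height (cm)} = \text{Height (inches)} * 0.3937" (formula markup left in). Pounds are converted to kilograms with 0.4536. BMI is weight in kg divided by the square of height in metres, and is then split at 30 kg/m².

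That split is used in three places:

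- **Subgroup.** Protocol section 7.5 and SAP section 7.2 name baseline BMI below 30 versus 30 or above as a subgroup. SAP section 9.4.5 says the main analysis "will be repeated on the primary estimand only using the subgroups defined in" section 7.2; the output is Table 14.2.1.6.3.
- **Covariate.** SAP section 7.2 lists "Body mass index (<30 kg/m², ≥30 kg/m²") as a candidate. Section 9.2 admits it by forward selection at p<0.05 and adds: "The covariates selected for this primary model will also be used in all other analytical models including covariates".
- **Demography.** SAP section 8.3 says age, sex, race and ethnicity "will be summarised together with height, weight and BMI at screening".

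Nothing else corrects the rule. Protocol section 6.2.3 says only that BMI is calculated from height and weight, and SAP Table 8 (changes from the protocol) does not mention it.

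Two smaller scoring entries belong with this point. In Appendix 7, "The Q29 score = $100*[x/5]$ where x=1-6 is the Q29 item value as above", and Q31 is scored the same way. In Table 10, the low cut-off for potentially clinically important glucose reads "Fasting glucose mg/dL mmol/L <0.17".

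**The concern.** The height factor runs the wrong way. Multiplying inches by 0.3937 gives an adult a height of roughly 23–30 cm. BMI squares that height, so the error is far too large for any plausible weight to offset. The pound factor beside it is right, so this is an isolated inversion.

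If the rule is programmed as printed, the ≥30 stratum becomes obese participants plus everyone measured in inches, and the <30 stratum keeps only people measured in centimetres. The BMI subgroup result for the primary endpoint would then mix obesity with recording unit. The recording unit may in turn follow country or site (SAP section 7.2 lists the UK, Poland, Hungary and the USA). The candidate covariate and the demography summary would be wrong too.

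Two programmers who both code from the SAP would agree with each other, so double programming need not reveal the error. The SAP describes no range check on derived height or BMI.

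**Working it through.** **Inputs from SAP 5.3.2:** factor 0.3937; pound factor 0.4536; BMI = kg / (cm/100)²; cut at 30. **Outside constant:** 1 inch = 2.54 cm.

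**1. The stated factor.** 1/2.54 = 0.39370, so the printed number is the cm-to-inch multiplier. It gives a correct height only as a divisor: 70/0.3937 = 177.8 cm. The pound factor checks (0.45359).

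**2. Size of the error.** Height is too small by 2.54/0.3937 = 6.4516. BMI is too large by 6.4516² = 41.62.

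| Height, weight | Height as printed | BMI as printed | Correct height | Correct BMI |
|---|---|---|---|---|
| 60 in, 100 lb | 23.6 cm | 812.9 | 152.4 cm | 19.5 |
| 65 in, 150 lb | 25.6 cm | 1039.0 | 165.1 cm | 25.0 |
| 70 in, 180 lb | 27.6 cm | 1075.0 | 177.8 cm | 25.8 |
| 78 in, 130 lb | 30.7 cm | 625.3 | 198.1 cm | 15.0 |

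**3. Can anyone measured in inches fall below 30?** The true BMI that maps to 30 is 30/41.62 = 0.72. In weight terms the limit is 30 × (inches × 0.3937/100)²: 1.56 kg at 58 in, 2.28 kg at 70 in, 2.69 kg at 76 in. So no adult can, whether weight was taken in kg or lb.

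**4. Share misclassified.** Let s be the share recorded in inches and q the share truly below 30. Neither is in the documents. If s = 0, nothing is affected. For illustration, assume s = 0.1 to 0.5 and q = 0.4 to 0.7, with recording unit independent of BMI.

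- Misclassified = s × q: from 0.1 × 0.4 = 4% to 0.5 × 0.7 = 35%, which is 9 to 79 of 225.
- Share of the ≥30 stratum that is truly below 30 = sq/(1−q+sq): from 0.04/0.64 = 6% to 0.35/0.65 = 54%.
- If the unit is also unrelated to the treatment effect, the subgroup difference retained is (1−q)/(1−q+sq): from 0.60/0.64 = 0.94 to 0.30/0.65 = 0.46. A true 10-point difference would read as 9.4 down to 4.6.

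**5. Vitality (Appendix 7).** Q23 and Q27 use 100 × (6−x)/5, which runs 0–100 for x = 1 to 6. Q29 and Q31 use 100 × x/5, which runs 20–120, so each is 20 too high. On a complete form the four-item average is (20+20)/4 = 10 too high, for a range of 10–110. A true move from 20 to 30 (+50%) becomes 30 to 40 (+33.3%). With two answered items the offset is 0, 10 or 20, depending on which two. Absolute change on complete forms is unaffected, but SAP section 9.6.1 also plans "Mean percentage change from baseline in Pain and Fatigue scores at Weeks 4, 8, 12, and 16".

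**6. Glucose (Table 10).** 0.17 mmol/L × 18.016 = 3.06 mg/dL, so the low flag would in practice never fire. In the same table, cholesterol at 7.77 mmol/L and triglycerides at 3.39 mmol/L both convert to 300 mg/dL, so those two entries look sound.

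**The case against.** The strongest reply is that the error is too conspicuous to survive. Minimum and maximum are reported for continuous variables, and the demography table is also an interim output. Heights near 28 cm and BMIs near 1000 would be hard to miss. The rule may simply be a slip for division by 0.3937. All of this stands as a reason to expect the error to be caught. It does not make the written rule right, and a silent repair in code would leave an undocumented departure from the SAP.

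Second, the documents say only that inches may be used. The affected share could be zero, and the figures in step 4 rest on assumed inputs. That is correct. The attenuation from 10 to 9.4–4.6 points is the weakest of them, because unit may follow country, and it should be read as illustration only. The 41.6-fold inflation and the reclassification of every participant measured in inches need none of these assumptions.

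Third, the reach is limited. No formal hypothesis is tested, BMI is one of three subgroup factors, it enters the primary model only if p<0.05, and section 9.4.3 allows troublesome covariates to be removed. This is accepted, and it is why nothing is claimed against the main result or the sample size.

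Fourth, the vitality and glucose items have no mechanism in common with height. They are real but separate and add no weight to the height point. Vitality is an exploratory score that is only summarised. For glucose, the normal-range shift table and the listings in section 10.5 still flag low values.

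**Conclusion.** The height rule in SAP section 5.3.2 is wrong as written and should be corrected. BMI is inflated 41.6-fold for anyone measured in inches, and all of them land in the ≥30 category, provided the formula is programmed literally. The harm depends on how many heights were recorded in inches, which the documents do not give; participants measured in centimetres are classified correctly.

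What is at risk is the BMI subgroup analysis of the primary estimand, the BMI candidate covariate (with its carry-over to other models if selected) and the height and BMI summaries. Height is a baseline value and the covariate is conditional, so no bias in the randomised primary contrast is asserted. Sample size and power do not depend on it.

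The vitality scoring error (complete scores exactly 10 too high) and the glucose cut-off (about 3 mg/dL) are also confirmed, each with limited reach.

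**What to change.** - **SAP 5.3.2:** Height (cm) = Height (inches) × 2.54. A range check on derived height and BMI would guard against a repeat.
- **Appendix 7:** score Q29 and Q31 as 100 × (x−1)/5, so that all four vitality items run 0–100.
- **Table 10:** re-derive the low fasting-glucose cut-off in mmol/L from the CTCAE v5.0 source named in section 10.5.
- **Section 9.6.2.1, check only:** in the text available for this review, each term of SE(log RR) appears as (1−n)/(nN). At 20/50 versus 15/75 the variance would be −19/1000 − 14/1125 = −0.031, against 0.6/20 + 0.8/15 = 0.083 from the usual formula. This may be a nested fraction flattened when the PDF was read, so it is not counted as an error. Look at the original layout and, only if it is as shown, use √[(1−n_A/N_A)/n_A + (1−n_P/N_P)/n_P].

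The cost is a few one-line SAP corrections and the matching derivation code, with no new data and no change to the design.
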